3.0 Endpoints

3.1 Primary Endpoint(s)

Resected Pancreatic Cancer Subjects

The primary endpoint is change in stool fat from Baseline (Day 1) to Week 1 (Day 8). Stool fat is collected during the 48 hours prior to the Day 1 and Week 1 visits.

3.2 Secondary Endpoint(s)

Resected Pancreatic Cancer Subjects

- Change from Baseline to Week 1 in average daily stool frequency. The average daily stool frequency is calculated from the last 3 days prior to each of Baseline and Week 1 visit.
- Change from Baseline to Week 1 in stool consistency, based on the proportion of days having watery stool consistency in the last 7 days prior to each of Baseline and Week 1 visit.
- Change from Baseline to Week 1 in the total EPI Symptoms Score.

3.3 Additional Endpoint(s)

Resected Pancreatic Cancer Subjects

- Average daily stool frequency for 7 days prior to each of Weeks 5, 9 and 13 visits compared to Baseline visit.
- Stool consistency in the 7 days prior to each of Weeks 5, 9 and 13 visits compared to Baseline visit.
- Total EPI Symptom Score at Weeks 5, 9 and 13 visits compared to Baseline visit.
- The scaled total score for each scale/item as described below of Quality of life (QoL) (European Organisation for Research and Treatment of Cancer [EORTC] Quality of Life Questionnaire [QLQ]-C30 and QLQ PAN26) at Weeks 1, 5, 9, and 13 visits compared to Baseline visit.

QLQ-C30:

- Global health status/QoL.
- Functional scales (Physical functioning, Role functioning, Emotional functioning, Cognitive functioning, Social functioning).
- Symptom scales/items (Fatigue, Nausea and vomiting, Pain, Dyspnoea, Insomnia, Appetite loss, Constipation, Diarrhoea, Financial difficulties).

QLQ-PAN26:

- Pancreatic Pain.
- Digestive symptoms (Gastrointestinal).
- Hepatic (Jaundice).
- Altered bowel habit.
- Poor body image.
- Satisfaction with health care.
- Sexuality (Sexual dissatisfaction).
- Body weight and body mass index (BMI) at Weeks 1, 5, 9 and 13 visits compared to Baseline visit.
- Chemotherapy tolerability (as defined in Section 9.4.6).
 - Difference in expected or planned chemotherapy from the last scheduled visit (Yes / No / Not Applicable, no chemotherapy planned) at Week 1, 5, 9 and 13 visits.
 - Proportion of expected or planned chemotherapy due to chemotherapy tolerability.
 - Proportion of different types of changes due to chemotherapy tolerability (entire regimen permanently discontinued / one or multiple agents permanently discontinued / dose held / dose interrupted / dose reduced / change in treatment administration schedule).
 - Diagnosis of changes due to chemotherapy tolerability (Adverse events / Medical history).
- Serum albumin and pre-albumin level at Weeks 1, 5, 9 and 13 compared to Baseline.

Non-Resected Pancreatic Cancer Subjects

- Change in stool fat from Baseline (Day 1) to Week 1 (Day 8).
- Change from Baseline to Week 1, 5, 9 and 13 in average daily stool frequency. The average daily stool frequency is calculated from the last 7 days prior to each of Baseline and Weeks 1, 5, 9, and 13 visits.

- Change from Baseline to Week 1, 5, 9, and 13 in stool consistency, based on the proportion of days having watery stool consistency in the last 7 days prior to each of Baseline and Week 1 visit.
- Change in the total EPI Symptoms Score from Baseline to Weeks 1, 5, 9, and 13.
- Change in scaled total score for each domain as described below of QoL (EORTC QLQ-C30 and QLQ-PAN26) from Baseline to Weeks 1, 5, 9, and 13.

QLQ-C30:

- Global health status/QoL.
- Functional scales (Physical functioning, Role functioning, Emotional functioning, Cognitive functioning, Social functioning).
- Symptom scales/items (Fatigue, Nausea and vomiting, Pain, Dyspnoea, Insomnia, Appetite loss, Constipation, Diarrhoea, Financial difficulties).

QLQ-PAN26:

- Pancreatic Pain.
- Digestive symptoms (Gastrointestinal).
- Hepatic (Jaundice).
- Altered bowel habit.
- Poor body image.
- Satisfaction with health care.
- Sexuality (Sexual dissatisfaction).
- Chemotherapy tolerability (as defined in Section 9.4.6).
 - Difference in expected or planned Chemotherapy from the last scheduled visit (Yes / No / Not Applicable, no chemotherapy planned) at Week 1,5,9 and 13 visits.
 - Proportion of expected or planned Chemotherapy due to chemotherapy tolerability.
 - Proportion of different types of changes due to chemotherapy tolerability (entire regimen permanently discontinued / one or multiple agents permanently discontinued / dose held / dose interrupted / dose reduced / change in treatment administration schedule).

- Diagnosis of changes due to chemotherapy tolerability (Adverse events / Medical history).
- Change in the following measurements from Baseline to Weeks 1, 5, 9, and 13: Body weight, and BMI.
- Change in the following measurements from Baseline to Week 5, 9, and 13 for serum albumin and serum pre-albumin level.

3.4 Safety Endpoint(s)

Safety endpoints will be based on evaluations including adverse events (AE) monitoring, physical examinations, vital sign measurements, and clinical laboratory testing (hematology, chemistry, and urinalysis). This information will be copied from the protocol.

4.0 Analysis Populations

The following population sets will be used for the analyses.

1. Intention to Treat (ITT)

The Intention to Treat (ITT) Set consists of all randomized subjects in the resected regimen and all enrolled subjects in the non-resected regimen. Subjects will be analyzed as randomized or enrolled. This population will be used to summarize subject disposition only.

The randomized treatment group in the resected regimen consists of the following groups:

- a. **High Dose:** Subjects randomized to Creon 72,000 dose cohort (72,000 USP units (Lipase) with meals/36,000 USP units (Lipase) with snacks)
- b. Low Dose: Subjects randomized to Creon 12,000 dose cohort (12,000 USP units (Lipase) with meals/6,000 USP units (Lipase) with snacks)

The treatment group in the non-resected regimen consists of all the subjects enrolled. All the subjects in this group will be receiving the High Dose of Creon 72,000 dose cohort (72,000 USP units (Lipase) with meals/36,000 USP units (Lipase) with snacks).

2. Full Analysis Set (FAS)

Resected and Non-Resected Subjects

The Full Analysis Set (FAS) includes all randomized or enrolled subjects who received at least one dose of study drug in the resected or the non-resected regimens, respectively. FAS will be used to summarize baseline characteristics unless it is specified otherwise.

3. Evaluable Analysis Set for Stool Fat Analysis (EAS-SF)

Resected and Non-Resected Subjects

The Evaluable Analysis Set for Stool Fat Analysis includes subjects from the FAS who have evaluable stool fat (see Section 9.3.2.1) at both Baseline and Week 1 visits.

4. Supplementary Analysis Set for Stool Fat Analysis (EAS-SF-SUPP)

The Supplementary Analysis Set for the Stool Fat Analysis includes subjects from the FAS in the resected regimen who have 100% stool sample collected for the 48 hour collection period at both Baseline (Day 1) and Week 1 visits (see Section 9.2.1).

5. Safety Analysis Set (Safety)

Resected and Non-Resected Subjects

The Safety Analysis Set will include all randomized/enrolled subjects who received at least one dose of study drug.

4.1 Analysis Treatment Groups

The following analysis treatment groups will be used in different analyses:

- 1. Analysis Treatment Group Per Day 1 Dispensing (ATG-Day 1, Resected and Non-Resected Regimen): These treatment groups will be determined by the actual study drug the subjects were dispensed at Day 1 visit.
 - a. **High Dose Group:** Subjects who were dispensed the high dose (72,000 USP units (Lipase) with meals/36,000 USP units (Lipase) with snacks) at the Day 1 visit.
 - Low Dose Group: Subjects who were dispensed the low dose (12,000 USP units (Lipase) with meals/6,000 USP units (Lipase) with snacks) at the Day 1 visit.
- 2. Analysis Treatment Group Per All Dispensing (ATG-All Dispensing, Resected regimen only): The following treatment groups will be determined by the actual study drug the subjects were dispensed throughout the study.
 - a. **High Dose:** Subjects who were dispensed the high dose (72,000 USP units (Lipase) with meals/36,000 USP units (Lipase) with snacks) at the Day 1 visit.
 - b. Low Dose: Subjects who were dispensed the low dose (12,000 USP units (Lipase) with meals/6,000 USP units (Lipase) with snacks) at the Day 1visit.
 - c. All low Dose: Subjects who were dispensed the low dose (12,000 USP units (Lipase) with meals/6,000 USP units (Lipase) with snacks) at all visits.
 - d. **Any High Dose:** Subjects who was dispensed the high dose (72,000 USP units (Lipase) with meals/36,000 USP units (Lipase) with snacks) at any of the visits.
- 3. Analysis Treatment Group Dynamic (ATG-Dynamic) per visit (Week 1, Week 5, Week 9, Week 13, Resected regimen only): These treatment group will be defined based on study drug dispensed to the subjects at the prior visit. For example, the dynamic treatment group at Week 1 visit would be based on the study drug dispensed to the subjects at Day 1 visit, which can be identified after unblinding by the kit number that had been dispensed to the subjects at Day 1 visit.

- a. **High Dose Group:** Subjects who was dispensed the high dose (72,000 USP units (Lipase) with meals/36,000 USP units (Lipase) with snacks) at the prior visit.
- b. Low Dose Group: Subjects who was dispensed the low dose (12,000 USP units (Lipase) with meals/6,000 USP units (Lipase) with snacks) at the prior visit.

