## 7.2 Definition for Analysis Populations

---

The full analysis set (FAS) includes all randomized subjects who received at least 1 dose of study drug. The FAS will be used for all efficacy and Baseline analyses. Subjects will be grouped according to treatment as randomized. Additional analysis population(s) may be used for the efficacy analysis. Details are provided in the SAP.

The safety analysis set consists of all subjects who received at least 1 dose of study drug. For the safety analysis set, subjects are assigned to a dose cohort based on the treatment actually received, regardless of the treatment randomized.

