1.0 Introduction

This Statistical Analysis Plan (SAP) describes the statistical analyses for CREON or ABT-SLV245 Study M16-142 titled "Creon® (pancrelipase) therapy for subjects with exocrine pancreatic insufficiency (EPI) due to pancreatic cancer: A double-blind, randomized, parallel design with 2 dose cohorts of pancrelipase in resected pancreatic cancer subjects and an open-label single dose cohort in non-resected pancreatic cancer subjects".

Study M16-142 examines the effects of Creon in subjects with resected pancreatic cancer receiving 2 dosing cohorts, and one dosing cohort in non-resected pancreatic cancer subjects.

The SAP will not be updated in case of administrative changes or amendments to the protocol unless the changes impact the analysis.

Unless noted otherwise, all analyses will be performed using SAS Version 9.4 (SAS Institute Inc., Cary, NC 27513) or later under the UNIX operating system.

This SAP includes changes to analyses described in the protocol version 3.0 dated 22 November 2019. Details are outlined in Section 12.0.

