4.2 Analysis Treatment Groups for Various Analyses

Table 1.Analysis Population and Analysis Treatment Groups for Various
Analyses

		R	esected	Non- Resected (All High Dose)
Analysis	Analysis Set	Analysis Treatment Groups	Treat Group Category	Analysis Treatment Groups
Disposition	ITT	As randomized	High Dose, Low Dose, Overall	As enrolled
Baseline Characteristics, Medical History, Prior and Concomitant Medications	FAS	ATG-Day 1	High Dose, Low Dose, Overall	ATG- Day 1
Drug Exposure	Safety	ATG-All Dispensing	High Dose, Low Dose, All Low Dose, Any High Dose, Overall	ATG- Day 1

Table 1.SA Analysis Treatment Groups for Various Analyses P Version
Summary History (Continued)

			R	esected	Non- Resected (All High Dose)		
Analysis		Analysis Set	Analysis Treatment Groups	Treat Group Category	Analysis Treatment Groups		
Drug Con	npliance (wee	k 1)	Safety	ATG-Day 1	High Dose, Low Dose, Overall	ATG- Day 1	
	Primary	stool fat (Week 1 within group)	EAS-SF, EAS-SF- SUPP	ATG-Day 1	High Dose, Low Dose	ATG- Day 1	
Efficacy	Secondary	stool fat (Week 1 between group)	EAS-SF, EAS-SF- SUPP	ATG-Day 1	High Dose, Low Dose	NA	
		Stool Frequency/Stool Consistency/EPI Symptom Week 1	FAS	ATG-Day 1	High Dose, Low Dose	ATG- Day 1	
	Efficacy		Stool Frequency/Stool Consistency by visit	FAS	ATG- Dynamic	High Dose, Low Dose, Overall	ATG- Day 1
	Additional	PRO by visit (EPI/PAN 26/C30)	FAS	ATG- Dynamic	High Dose, Low Dose, Overall	ATG- Day 1	
		BMI/Weight by visit	FAS	ATG-All Dispensing	High Dose, Low Dose, All Low Dose, Any High Dose, Overall	ATG- Day 1	

Table 1.SA Analysis Treatment Groups for Various Analyses P Version
Summary History (Continued)

				R	esected	Non- Resected (All High Dose)
Analysis			Analysis Set	Analysis Treatment Groups	Treat Group Category	Analysis Treatment Groups
Efficacy Additional	Albumin and pre-albumin by visit	FAS	ATG-All Dispensing	High Dose, Low Dose, All Low Dose, Any High Dose, Overall	ATG- Day 1	
	Chemotherapy tolerability by visit	FAS	ATG-All Dispensing	High Dose, Low Dose, All Low Dose, Any High Dose, Overall	ATG- Day 1	
		AE/SAE in Week 1	Safety	ATG-Day 1	High Dose, Low Dose, Overall	ATG- Day 1
Safety		AE/SAE analyses (entire treatment period)	Safety	ATG- Dynamic	High Dose, Low Dose, Overall	NA
		All other AE/SAE analysis	Safety	ATG-All Dispensing	High Dose, Low Dose, All Low Dose, Any High Dose	ATG- Day 1
		Lab / Vital Signs	Safety	ATG-All Dispensing	High Dose, Low Dose, All Low Dose, Any High Dose	ATG- Day 1

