Appendix A. Protocol Deviations

The number and percentage of subjects who reported at least one of the following protocol deviation categories will be provided.

- Subject entered into the study even though s/he did not satisfy entry criteria.
- Subject developed withdrawal criteria during the study and was not withdrawn.
- Subject received wrong treatment or incorrect dose of study.
- Subject took prohibited concomitant medication.

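### SAP groups the baseline table and the Week 1 between-dose comparisons by drug dispensed at Day 1, where the protocol says as randomized

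*SAP*

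**What the plan says.** **Protocol 7.2** sets two rules. For efficacy, "The FAS will be used for all efficacy and Baseline analyses", and "Subjects will be grouped according to treatment as randomized". For the safety set, "subjects are assigned to a dose cohort based on the treatment actually received, regardless of the treatment randomized". Treatment received is thus reserved for safety.

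**SAP 4.1** defines ATG-Day 1: "These treatment groups will be determined by the actual study drug the subjects were dispensed at Day 1 visit".

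**SAP Table 1 (Section 4.2)** applies ATG-Day 1 in the resected population to:
- baseline characteristics, medical history, and prior and concomitant medications;
- the primary within-group stool fat analysis;
- the secondary row that begins "stool fat (Week 1 between group";
- stool frequency, stool consistency and EPI symptoms at Week 1.

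The only row grouped as randomized is disposition. SAP 4.0 says of the set analyzed that way: "This population will be used to summarize subject disposition only".

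**SAP 1.0** says that this SAP changes analyses described in the protocol and adds: "Details are outlined in Section 12.0". Section 12.0 concerns type I error control and does not mention treatment grouping. Nor does the version history in Section 13.0.

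**The concern.** The Week 1 comparisons are the only formal between-dose efficacy tests in the SAP; later visits are summarized descriptively. Protocol 4.2 calls the low dose the control group, and the sample size section gives power for the stool fat difference. These are therefore the places where randomization supports the inference.

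Once a subject is counted under the dose handed out instead of the dose allocated, the ANCOVA difference and the rank-sum comparison are as-treated. The baseline table, grouped the same way, no longer describes the arms that randomization formed. The SAP defines the two groupings separately and plans no as-randomized efficacy result, so a reader of the report could not see whether the choice mattered.

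**Working it through.** **Inputs**
- 72 resected subjects, 36 per dose, 16% dropout, 60 evaluable, so 30 per arm (Protocol 7.3, SAP 2.4).
- Between-dose difference 20 g or 15 g, SD of change 25 g in both groups, two-sided 0.05 (same sections).
- Number of subjects dispensed the other dose at Day 1: not given. A range is assumed below.

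**1. The plan's own figures reproduce.** Dropout: 60/(1 − 0.16) = 71.4, rounded up to 72. A two-sample t-test with 30 per arm and SD 25 g (noncentral t) has power 86.1% at 20 g and 62.8% at 15 g, against the stated 86% and 63%. If every Day 1 kit matches the allocation, the two groupings are identical and none of these figures changes.

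**2. Who can be moved.** ATG-Day 1 depends only on the dose dispensed at Day 1. A wrong kit containing the same dose moves nobody. Errors at Weeks 1, 5 or 9 do not enter ATG-Day 1. Only a Day 1 error in which the other dose is dispensed counts.

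**3. Bias from grouping as dispensed.** Suppose *k* subjects randomized to low dose are dispensed high dose, and their change differs from the arm mean by *b* for reasons unrelated to dose. The groups become 30 + *k* and 30 − *k*, and the difference shifts by

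bias = *kb*/(30 + *k*) + *kb*/(30 − *k*)

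| *k* | *b* | Calculation | Bias | Share of 20 g |
|---|---|---|---|---|
| any | 0 g | 0 | 0 g | 0% |
| 1 | 25 g | 25/31 + 25/29 | 1.7 g | 8% |
| 2 | 25 g | 50/32 + 50/28 | 3.3 g | 17% |
| 1 | 50 g | 50/31 + 50/29 | 3.3 g | 17% |
| 2 | 50 g | 100/32 + 100/28 | 6.7 g | 33% |

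Here 25 g is one planned SD and 50 g is two, so the 50 g rows are extreme. The table covers subjects moved in the same direction. With one subject moved each way, the shifts can add or cancel.

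**4. What as-randomized grouping would show instead.** Suppose *m* of 30 subjects in each arm receive the other dose, with no prognostic difference. The as-randomized difference is 20 × (1 − 2*m*/30).

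| *m* per arm | Difference | Power (SD held at 25 g) |
|---|---|---|
| 0 | 20.0 g | 86% |
| 1 | 18.7 g | 81% |
| 2 | 17.3 g | 75% |
| 3 | 16.0 g | 68% |

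As-dispensed grouping would still show 20 g. So even without bias, the two groupings answer different questions once a cross-dose error occurs, and the SAP's choice gives the larger difference.

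**The case against.** **The trigger is unlikely.** IRT assigns the kit (Protocol 5.6), and nothing may be dispensed without contacting IRT (Operations Manual 6.1). Active and placebo capsules look identical and sites are blinded, so a site could not choose a dose according to prognosis. This stands: such errors are probably rare, and any that occur may be close to random.

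**The deviation category.** SAP Appendix A counts "Subject received wrong treatment or incorrect dose of study". A reader might infer that the sponsor expects Day 1 cross-dose errors. The text does not support that. It is a general category for the whole study, and shows only that allocation and treatment can differ.

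**Regrouping need not bias.** A subject whose change differs only because of the other dose is not a source of bias when counted under that dose. This stands, and is why *b* is limited to differences unrelated to dose.

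**ATG-Day 1 has a practical purpose.** It sits beside two groupings that handle later escalation, and SAP 7.2 treats Day 1 dispensing as the same event as randomization. The sponsor may have meant it as a stand-in for the randomized arm. That may explain the choice, but the definition as written rests on the drug dispensed.

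**The protocol allows additional efficacy populations.** That concerns who is included. It does not change the arm in which a subject is counted.

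**The stakes are limited.** The comparisons are secondary, there is no multiplicity control, and SAP 12.0 says that the study is not for registration. All of this stands.

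**Conclusion.** The protocol and SAP contradict each other on treatment grouping for the baseline table and the Week 1 between-dose comparisons, and the change is neither listed nor justified. The SAP should be corrected.

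The numerical effect is conditional. It is nil without a Day 1 cross-dose error. With one or two subjects moved the same way and 30 evaluable per arm, it ranges from zero to about 6.7 g, depending on an assumed deviation of 0 to 50 g unrelated to dose.

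Two stronger readings go too far. A reader might infer that any dispensing error breaks the randomized comparison; only a Day 1 error that crosses doses moves anyone. A reader might also infer that the primary result loses its randomized basis; the primary test is a change from Baseline within each dose cohort and never was a randomized contrast. What remains is an inconsistency that is cheap to remove now and harder to defend after unblinding.

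**What to change.** In SAP 4.1 and Table 1:

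1. Use as-randomized grouping for resected baseline characteristics and for all Week 1 between-dose efficacy comparisons (stool fat, stool frequency, stool consistency, EPI score).
2. Keep ATG-Day 1 for safety and Week 1 exposure.
3. Report how many subjects were dispensed the other dose at Day 1.
4. Show ATG-Day 1 as an efficacy sensitivity analysis only if that number is above zero.

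SAP 9.4.1 takes the between-dose stool fat difference from the same ANCOVA as the primary within-cohort means. It is simplest to change the primary row too, which Protocol 7.2 also covers.

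The cost is an edit to one column of Table 1 and one added count. It needs no new data, no more subjects and no protocol amendment, since the protocol already states this rule. Sample size and planned power are unchanged.

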2.5 Dose Modification

Dose modifications will be determined by a "dispensation score" calculated in EDC based on the responses to Questions 7, 8 and 10 from the EPI Symptom Questionnaire (Appendix D). The "dispensation score" will be then entered in IRT by the sites. Whether the subject needs dose modification will be determined by the "dispensation score" and IRT will then dispense the corresponding drug accordingly. The process will keep the site staff and the subjects blinded on whether the subject will be dose modified or not. The dose modification process including the details of the IRT dispensation score derivations are documented in the Study M16-142 Documentation of Key Decision dated 09 February 2020. The general dose modification rules are described as below.

Calculation of Total Score for Dose Modification:

The score for dose modification will be calculated by assigning the following values to each one of the responses to Questions 7, 8, and 10 in the EPI symptom questionnaire: none = 0, mild = 1, moderate = 2, severe = 3, very severe = 4. The total score for dose modification will be calculated as the sum of the responses to Questions 7, 8, and 10 within each visit. If none of the three questions are answered, the score will be noted as NULL.

The criteria for dose modification are described below:

- a. If current score = NULL, then maintain dose.
- b. If the previous score is NULL and the score for the current visit is available, then replace the previous score with the last available visit score as the previous score and follow the dose escalation criteria d) e) or f).
- c. If the Baseline visit score and all other visit scores prior to the present visit are NULL but the present visit score is available, then maintain dose.
- d. If current score <= 2, then maintain dose.
- e. If current score > 2 and there is less than 30% improvement from the previous score, i.e., current score > $(0.7 \times \text{previous score})$, then increase dose.

f. If current score > 2 and there is 30% or more improvement from the previous score i.e., current score <= $(0.7 \times \text{previous score})$, then maintain dose.

The subjects, site staffs and Abbvie site monitors will be blinded to the detailed dose modification criteria as well as the subject's dose medication status.

Resected Subjects

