The dose for resected subjects in the low dose cohort (12,000 USP units (Lipase) with meals/6,000 USP units (Lipase) with snacks) will be modified to the high dose (72,000 USP units (Lipase) with meals/36,000 USP units (Lipase) with snacks) at Week 1, 5, or 9 if the dose modification criteria defined above are met. Subjects randomized to the high dose cohort are not dose modified.

Only one dose modification will be permitted throughout the study. For subjects who have already experienced dose escalation, they will remain on the high dose level for the rest of the treatment duration, even if they continue to meet the dose escalation criteria in the subsequent visit(s). No further dose escalation is allowed.

Non-Resected Subjects

Non-resected subjects in the open-label population will continue to receive pancrelipase at a dose of 72,000 USP units (Lipase) with meals/36,000 USP units (Lipase) with snacks during the study; there will be no dose modification.

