9.4.2 Stool Frequency

Stool frequency is collected each day for 7 days prior to each visit during the study period. For the analysis, the average number of stool frequency per day is considered for the last 3 days prior to each visit (Day –3 to Day –1 for Baseline and Day 5 to Day 7 for Week 1 visit). The average stool frequency per day for a visit is defined as total number of stools in the last 3 days divided by 3 for that visit.

The analyses will be performed using the population and treatment groups as described in Table 1 in Section 4.2.

- For analysis of change in stool frequency from Baseline to Week 1, both within dose cohort and for comparison between dose cohorts (resected regimen only), an ANCOVA model including treatment as a fixed effect (resected population only) and Baseline stool frequency as the covariate will be used. Day -3, Day -2 and Day -1 would be considered for Baseline and Day 5, Day 6 and Day 7 would be considered for Week 1 visit.
- Descriptive summary statistics will be provided for change in stool frequency from Baseline to Week 1, 5, 9 and 13. For the summary, the average stool frequency per day for the Baseline and Week 1 is defined as total number of stool frequency in the last 3 days divided by 3 for that visit for comparison to Week 1. However, the average stool frequency per day for the Baseline and Week 5, 9 and 13 is defined as total number of stool frequency in the last 7 days divided by 7 for that visit for comparison to all other post-baseline visits.

• Descriptive statistics per day for stool frequency are presented specifying the mean, standard deviation, median, minimum and maximum of stool frequency for 7 days prior to Baseline and Week 1.

Sensitivity Analysis for Stool Frequency:

- For the sensitivity analysis, the average number of stool frequency per day is considered for the last 7 days prior to each visit. The average stool frequency per day for a visit is defined as total number of stool frequency in the last 7 days divided by 7 for that visit. Day -7 to Day -1 would be considered for Baseline and Day 1 to Day 7 would be considered for Week 1 visit.
- The 7-day mean will be analyzed similar to the primary analysis of the stool frequency using an ANCOVA model including treatment as a fixed effect (resected population only) and Baseline stool frequency as the covariate. Summary statistics and comparing the change in stool frequency from Baseline to Week 1 will also be summarized.

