9.4.3 Stool Consistency

Stool consistency will be collected once a day for 7 days prior to each visit using the Bristol Stool Chart and will be characterized based on the typology below for the analysis. The proportion of days with watery consistency during 7-day period prior to each visit will be calculated at each visit for each subject. The analyses will be performed using the population and treatment groups as described in Table 1 in Section 4.2.

- A Wilcoxon paired signed rank test will be performed for comparison of the proportion of days with watery stool consistency of Week 1 to that at Baseline within each dose cohort in the resected population. Similar test will be performed in the non-resected population as well.
- For comparison of change in the proportion of days with watery stool consistency from Baseline to Week 1 between two dose cohorts will be assessed through the non-parametric Wilcoxon Rank-Sum test in the resected population.

- Descriptive statistics will be provided for proportion of days with watery stool consistency at Week 1 (Day 8), 5, 9 and 13 as well as change from Baseline for each visit in both the resected and non-resected population.
- The number and percentages of subjects with 7 different types of stool consistency reported and 2 different types of characterization of stool consistency as described in Table 3 will be summarized per day for 7 days prior to Baseline (Day 1) and 7 days prior to Week 1 (Day 8) visit for the non-resected population and for each analysis treatment group in the resected population.

Table 3. Characterization of Bristol Stool Chart for Analysis

Stool Type (Score)	Characterization
Type 1 (1), Type 2 (2), Type 3 (3), Type 4 (4), Type 5 (5)	Hard/Normal
Type 6 (6), Type 7 (7)	Watery

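### From Week 5, the resected stool and patient-reported outcome tables split dose groups only by drug currently dispensed, so a symptom rule decides which low-dose starters stay in the Low column

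*SAP*

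**What the plan says.** SAP 4.1 defines ATG-Dynamic for resected subjects: "These treatment group will be defined based on study drug dispensed to the subjects at the prior visit". The Week 1 column follows Day 1 dispensing, the Week 5 column follows Week 1 dispensing, and so on.

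In SAP 4.2, Table 1, two efficacy rows use ATG-Dynamic with the columns High Dose, Low Dose and Overall: "Stool Frequency/Stool Consistency by visit" and "PRO by visit (EPI/PAN 26/C30". SAP 9.4.2 to 9.4.5 refer back to Table 1 and add no other dose split after Week 1.

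SAP 2.5 sets the escalation rule on the sum of EPI Questions 7, 8 and 10, which runs from 0 to 12. The dose goes up under this condition: "If current score > 2 and there is less than 30% improvement from the previous score". Movement is one way: "Subjects randomized to the high dose cohort are not dose modified".

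The affected endpoints include "Total EPI Symptom Score at Weeks 5, 9 and 13 visits compared to Baseline visit" (SAP 3.3). The stool sections plan, for frequency, "Descriptive summary statistics will be provided for change in stool frequency from Baseline to Week 1, 5, 9 and 13", and for consistency the "proportion of days with watery stool consistency at Week 1 (Day 8), 5, 9 and 13 as well as change from Baseline".

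Protocol 7.2 says that full-analysis-set efficacy subjects are grouped as randomised. SAP 1.0 says its changes from the protocol are set out in Section 12.0, but that section covers only Type I error and does not mention grouping.

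**The concern.** Column membership depends on earlier values of what is being tabulated. Questions 7 (foul-smelling stools), 8 (greasy stools) and 10 (diarrhea) are three of the twelve items in the EPI total. They are also close to stool consistency, stool frequency and the bowel items of the two EORTC questionnaires. Low-dose starters whose symptoms persist leave Low and enter High, while high-dose starters with the same symptom course stay where they are. After Week 1 neither column is a randomised group.

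A reader who sees High and Low side by side at Weeks 5, 9 and 13 will tend to read the gap as a dose effect, and the layout does not support that reading. The Overall column is not affected, but it does not separate the doses. The SAP does not treat every outcome this way: weight and BMI, albumin and pre-albumin, and chemotherapy tolerability use ATG-All Dispensing, which keeps High and Low columns fixed by Day 1 dispensing. Those columns are missing from the tables where the selection acts most directly.

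**Working it through.** **Plan's own figures.** The documents give no expected escalation rate and no between-dose figure after Week 1, so there is nothing to reproduce for these visits.

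**Step 1: timing.** The Week 1 score decides the Week 5 column, the Week 5 score the Week 9 column, and the Week 9 score the Week 13 column. At Week 1, ATG-Dynamic equals Day 1 dispensing, so the problem starts with the Week 5 table.

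**Step 2: what a subject must do to stay Low.** A low-dose starter escalates if score > 2 and score > 0.7 × previous score. In integers, the second condition is 10 × score > 7 × previous. With complete questionnaires, a subject can stay Low with a score above 2 only after a fall of at least 30% at every visit so far. Starting from the maximum of 12:

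- Week 1: 0.7 × 12 = 8.4, so at most 8
- Week 5: 0.7 × 8 = 5.6, so at most 5
- Week 9: 0.7 × 5 = 3.5, so at most 3

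**Step 3: enumerating all score paths (each score 0 to 12).**

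| Table | Paths that stay Low | Of these, last score above 2 | Highest last score in Low | Cap for randomised high-dose subjects |
|---|---|---|---|---|
| Week 5 | 67 of 13² = 169 | 28 (Baseline at least 5) | 8 | none |
| Week 9 | 223 of 13³ = 2,197 | 22 (Baseline at least 8) | 5 | none |
| Week 13 | 670 of 13⁴ = 28,561 | 1 | 3 | none |

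These count possible paths; they are not probabilities.

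- The single Week 13 exception is 12-8-5-3: 80 ≤ 84, 50 ≤ 56, 30 ≤ 35. Everyone else in that Low column scored 2 or less at Week 9.
- Path 12-8-6 stays Low at Week 1 (80 ≤ 84) but escalates at Week 5 (60 > 56). It enters High in the Week 9 table although its score has halved since Baseline.
- If one questionnaire is missed, rules a to c of SAP 2.5 can keep a subject on the low dose and the caps rise to 12, 8 and 5. For example, with Baseline missing, a Week 1 score of 12 maintains the dose.

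**Step 4: effect on the tabulated outcome (assumed inputs).** The simulation had no dose effect, 60,000 subjects per arm, 12 items scored 0 to 4, and 240 scenarios. Assumptions not in the documents:

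- mean baseline rule score about 3.2 to 7.5
- within-subject correlation 0.4, 0.6 or 0.8 (exchangeable or AR(1))
- between-item correlation 0.3 or 0.6
- latent improvement of 0, 0.5 or 1.0 point per item by Week 13 (early or even)
- no dropout

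| Table | Low-dose starters still Low | Low minus High, EPI change from Baseline |
|---|---|---|
| Week 5 | 6–80% | -7.3 to +0.2 |
| Week 9 | 0.4–70% | -7.0 to +1.6 |
| Week 13 | 0–65% | -3.6 to +2.7 |

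The gap ranges use scenarios with at least 4 of 36 still Low. The EPI total runs from 0 to 48, and a negative gap favours Low. The largest gap was about 1.9 standard errors with 36 per arm.

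A separate, narrower simulation (mean baseline EPI total 16 to 19.5, no dose effect) also grouped the same subjects by Day 1 dispensing. The High versus Low difference in EPI total was then within 0.1 point at every visit. Under ATG-Dynamic, the gap in EPI change favoured Low by 0.7 to 2.6 points at Week 5. At Week 13 it ranged from 0.7 in favour of Low to 1.6 in favour of High. Stool and quality-of-life endpoints were not simulated.

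**The case against.** The best defence is that no planned contrast is harmed. Protocol 3.3 asks for a between-dose difference only at Week 1, and at later visits the comparison is with Baseline. The SAP lists the later visits as Additional endpoints, summarises them descriptively, and bases the Week 1 comparisons on Day 1 dispensing. ATG-Dynamic is openly defined, and grouping by the drug in use is a recognisable descriptive choice. Protocol 7.3 leaves details of other efficacy analyses to the SAP. As-randomised columns would not estimate a fixed-dose effect either.

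The size is also uncertain. The caps loosen with missed questionnaires, and the simulated ranges cross zero at all three visits. In a similar no-effect grid of 300 scenarios, the median Low minus High gap was -1.9 at Week 5, -0.4 at Week 9 and +0.25 at Week 13. Gaps were below 2 points in 84% of scenarios at Week 9 and 91% at Week 13, and the extremes came from a corner with high baseline scores and weak correlation.

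Most of this stands, and it limits the weight of the point. It does not remove it. Side-by-side dose columns invite a comparison whether or not a test is planned, and even change from Baseline within a column describes a selected and changing group. That size and sign cannot be predicted is itself the reason the gap cannot be read as dose. Protocol 3.3 still lists the Week 5, 9 and 13 results as secondary, and EPI symptoms are named in the study objective. The SAP's stated reason for dynamic grouping, unequal exposure time, is given for adverse event rates in 10.2.1.2 and not for efficacy.

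**Conclusion.** The concern holds, with high confidence on structure and mechanism. From Week 5, differences between the High and Low columns in the stool, EPI and quality-of-life tables mix dose with selection on symptom response. The caps of 8, 5 and 3 of 12 are exact, given complete questionnaires. The gap in EPI change depends on inputs the documents do not give and can take either sign; the ranges above illustrate it and do not predict it. For the EPI total and stool frequency only change from Baseline is planned, while stool consistency and the quality-of-life scales are tabulated as levels as well.

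Consequences are limited to descriptive tables of Additional endpoints. The primary endpoint, all Week 1 analyses and the Overall column are not touched. This is a change that should be made, not one on which the trial's main conclusion depends.

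**What to change.** In the two Table 1 rows, add High and Low columns as randomised (or by Day 1 dispensing), as ATG-All Dispensing already does for weight and BMI, albumin and chemotherapy tolerability, and in line with Protocol 7.2. Report the number escalated at each visit: the All Low Dose group in the Drug Exposure row gives only the total, and ATG-Dynamic column sizes show the movement only approximately because of dropout. Keep ATG-Dynamic as a supplementary display, labelled as non-randomised and not for comparing doses. State the departure from Protocol 7.2 where the SAP lists its changes.

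The cost is Table 1 wording and one more set of descriptive tables. The real downside is that the as-randomised Low column describes a strategy of starting low and escalating if the criteria are met. It is diluted by escalation (35–100% escalated before the Week 13 table across the assumed inputs) and says little about continuous low dose. It does keep the randomised comparison, which ATG-Dynamic does not.
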